1.1.1 Multiple Fraction SBRT (for peripheral lesions)

Onishi et al. reported outcomes among 257 patients treated in 14 Japanese centers with SBRT using many dosing schemes (1-22 fractions at 3-12 Gy per fraction). Total dose ranged from 18 to 75 Gy. With 38 months median follow-up, patients receiving a biologically equivalent dose (BED) of >100 Gy experienced fewer local recurrences than those patients receiving < 100 Gy BED (42.9 vs 8.1%, p<0.001.) Similarly, survival was significantly improved with higher BED doses, 70.8 vs. 30.2% (p<0.05.) grade 3 or higher toxicity was observed in 5.4% ²⁶.

Echoing these results, Wulf et al. studied the dose-response for local tumor control after SBRT in 92 pulmonary tumors (36 NSCLC and 56 metastases.). Short course irradiation of 1-8 fractions with different fraction doses was used. After a median follow-up of 14 months (2-85 months) 11 local recurrences were observed. A BED dose of 94Gy at the isocenter and 50Gy at the PTV-margin were demonstrated to give 50% probability of tumor control (TCD50). Multivariate analysis revealed the dose at the PTV-margin as the only significant factor for local control. No severe toxicity was observed²⁷.

While the initial experience with multi-fraction SBRT regimens as summarized above showed very little toxicity, more recent publications have shown higher rates of toxicity, likely somewhat secondary to more rigorous reporting of toxicities in more recent trials.

Baumann et al. reported on 138 patients with stage I NSCLC treated with SBRT delivered using a 3D conformal multifield technique and a stereotactic body frame. Doses delivered were 30-48 Gy (65% isodose at the periphery of PTV) in 2-4 fractions. Equivalent dose in 2 Gy fractions (EQD2) was in the range of 50-100 Gy. Three- and 5-year overall survival was 52 and 26% respectively. Lung cancer specific 3- and 5-year overall survival was 66 and 40% respectively. EQD2 (> vs <55.6 Gy) showed a statistically significant survival benefit for the higher doses. Fifty nine percent (83/138) of the patients had no side effects. Fourteen patients (10%) experienced RTOG grade 3-4 toxicity²⁸.

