1.3 Roswell Park Cancer Institute Experience to Date

Since March 2006 we have treated 23 NSCLC patients with SBRT (60 Gy in 3 fractions.) No significant toxicities have been seen.

In addition, Cleveland Clinic is a high volume center for SBRT. They have expressed an interest in joining this study. The administrative process is underway. For this reason the stratification variables were changed to performance status and treatment center.

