2.1.1 To compare incidence of toxicity with two established SBRT regimens for NSCLC

2.2 Secondary:

2.2.1 To compare QOL, patterns of failure, disease free survival, and overall survival associated with 2 two established SBRT regimens for NSCLC

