6.0 TREATMENT PLAN

6.1 Study Design

Medically inoperable patients with node negative, peripherally located, biopsy proven NSCLC measuring ≤5 cm will be enrolled, stratified, and randomized to receive multi-fraction or single fraction SBRT.

Patients will be stratified by KPS into one of three groups (See Appendix IV) and treatment center. (100, 90, 80 and below).

Prior to SBRT delivery, patients will undergo baseline imaging using PET/CT and will undergo formal pulmonary function testing. Blood and

urine samples will also be formally collected and stored for future correlative studies.

Patients randomized to the multi-fraction arm will receive 3 high dose fractions of radiation to the primary lung tumor. Those randomized to the single fraction arm will receive a single high dose fraction using SBRT. Overall treatment time for one fraction is one day, for three fractions is 8-24 days. Treatment may start within 4 weeks after registration.

SBRT is a technique that allows for improved precision of radiation delivery. In order to deliver stereotactic radiotherapy, precise mechanisms of patient immobilization, tumor localization, and beam delivery are required and discussed in detail below.

Following SBRT delivery, imaging and pulmonary function studies will be regularly performed to monitor tumor status and toxicity. Blood and urine, samples may also be formally collected and stored, as described above, following SBRT and in the event of tumor recurrence such that correlative studies can be performed.

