7.0 STUDY CALENDAR

	Pre- Treatment ¹¹	Rx #1 ¹⁰	Rx #2	Rx #3 ⁹	6 wks post- rx	12 wks post- rx	f/u ^{1,11}
H&P ⁸	X	Х	Х	Х	Х	Х	Х
Performance Status	X	X	X	X	X	Х	Х
Evaluation by Thoracic Oncologist	X						
Evaluation by Radiation Oncologist	X						
Pregnancy test	X						
CT C/A/P ⁷	X						
PET-CT scan ⁷	Х						X ²
PFT's ⁶	X						X ³
Tumor Biopsy	X						X4
Blood and urine, collection for DBBR, future analyses ⁵	X						
Toxicity Eval	X	Х	Х	Х	Х	Х	Х
QOL questionnaire	X	X	X	X	X	X	X

¹ At week 6 and 12 post SBRT as noted above, then every 3 months for 1 year, and every 6 months for the next 4 years. Patients will be followed for a total of 5 years.

² PET-CT will be done at 6 months and then as clinically indicated

³ PFTs will be done at 6 months, and annually in follow-up

⁴ Biopsies will be done only if clinically indicated.

⁵Blood and urine will be collected through the DBBR at pre-treatment. Patients may refuse this and still participate in the study. This will not be offered at network sites.

⁶ Full Spirometry and DLCO

⁷ Any one of these pre-treatment imaging studies should be done within 6 weeks of registration: CT Chest, PET or CT Simulation

⁸ H&P within 2 weeks of treatment start

⁹Overall treatment time for one fraction is one day, for three fractions is 8-24 days.

¹⁰Treatment may start within 4 weeks after registration.

¹¹Pre-treament and follow up assessments may be waived at the discretion of the Principal Investigator.

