12.0 STATISTICAL ANALYSIS

This is a phase II randomized study to compare incidence of RTOG grade 3 or higher toxicity associated with 2 different, established SBRT regimens for NSCLC.

Group sample sizes of 49 in group one (Gy x 3) and 49 in group two (Gy x 1) achieve 81% power to detect a difference between the group incidences of toxicity of 0.17. The incidence of toxicity in group one (the treatment group) is assumed to be 0.03 under the null hypothesis and 0.2000 under the alternative hypothesis. The proportion in group two (the control group) is 0.03. The test statistic used is the one-sided Z test with continuity correction and unpooled variance. The significance level of the test was targeted at 0.05. The significance level actually achieved by this design is 0.0037.

Descriptive statistics will be presented for each group. Incidence of toxicity will be compared using Z test. Disease free survival and overall survival will be compared between two groups using log-rank test statistics. Correlation analysis will be performed to explore the relationship between outcomes and toxicities with tumor biomarkers. The estimate of acute and long term toxicity associated with SBRT for NSCLC will be reported.

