APPENDIX IV KARNOFSKY PERFORMANCE STATUS SCALE DEFINITIONS RATING (%) CRITERIA

	100	Normal no complaints; no evidence of disease.					
Able to carry on normal activity and to work; no special care needed.	90	Able to carry on normal activity; minor signs or symptoms of disease.					
	80	Normal activity with effort; some signs or symptoms of disease.					
	70	Cares for self; unable to carry on normal activity or to do active work.					
Unable to work; able to live at home and care for most personal needs; varying amount of assistance needed.	60	Requires occasional assistance, but is able to care for most of his personal needs.					
		Requires considerable assistance and frequent medical care.					
	40	Disabled; requires special care and assistance.					
Unable to care for self; requires equivalent of institutional or hospital care; disease may be progressing rapidly.	30	Severely disabled; hospital admission is indicated although death not imminent.					
	20	Very sick; hospital admission necessary; active supportive treatment necessary.					
	10	Moribund; fatal processes progressing rapidly.					
		Dead					

References:

de Haan R, Aaronson A, et al. Measuring quality of life in stroke. Stroke. 1993; 24:320-327.

Oxford Textbook of Palliative Medicine, Oxford University Press. 1993;109.

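### Randomisation is stratified by KPS and centre, but the DFS and OS log-rank test names neither factor; a KPS-stratified test should be specified

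*Combined protocol and SAP*

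**What the plan says.** Section 6.1 sets the randomisation strata: "Patients will be stratified by KPS into one of three groups (See Appendix IV) and treatment center". The three KPS groups are 100, 90, and 80 and below. Section 1.3 shows that the choice was deliberate. When a second high-volume centre was expected to join, the text records: "For this reason the stratification variables were changed to performance status and treatment center".

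DFS and OS are secondary objectives (Section 2.2.1): "To compare QOL, patterns of failure, disease free survival, and overall survival associated with 2 two established SBRT regimens for NSCLC". Their whole analysis is one sentence in Section 12.0, repeated in the abstract: "Disease free survival and overall survival will be compared between two groups using log-rank test statistics". It names no strata, covariates, hazard ratio, Cox model, sidedness or significance level. Nowhere do the documents use KPS or centre in an analysis.

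**The concern.** Stratified randomisation makes the arms alike on KPS. A plain log-rank test takes no account of that. Its variance still allows for chance KPS imbalance that the design has largely removed, and it compares patients of different KPS within the same risk sets. If KPS predicts survival, three things follow:

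- the actual type I error falls below the nominal level;
- power falls;
- an unstratified hazard ratio lies closer to 1 than the hazard ratio among patients of the same KPS.

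Type I error is not inflated. The possible harm is lost sensitivity in a small comparison of 98 patients with about 60 deaths, although KPS group is already known for every randomised patient. Silence also leaves the choice between a plain, a KPS-stratified and a KPS-by-centre test open until the data can be seen.

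**Working it through.** **The plan's own figure.** Section 12.0 gives power only for toxicity. Exact enumeration of two binomial arms of 49 (0.20 vs 0.03; one-sided Z test with continuity correction and unpooled variance) gives power 80.5% and level 0.0037, against the stated 81% and 0.0037. It reproduces, with about 49 × 0.20 + 49 × 0.03 = 11.3 events expected. No power, event count or hazard ratio is stated for DFS or OS.

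**Inputs from the documents.**
- 98 patients, allocated 1:1 (Section 12.0).
- Five-year OS of 26% in one arm, from the Nordic series in Section 1.1.1: "Three- and 5-year overall survival was 52 and 26% respectively".
- Censoring at five years (Section 7.0): "Patients will be followed for a total of 5 years".

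**Assumptions the documents do not supply.**
- Hazard ratio 0.5 and two-sided 5%.
- Five centres holding 50/20/10/10/10% of patients, and permuted blocks of 4 within KPS by centre.
- Exponential survival, with the hazard multiplied by 1, 1.5 or 2 per KPS step.
- KPS mix of equal thirds, or 5/35/60% for 100/90/80 and below. The second mix reflects the Appendix IV definition of KPS 100, "Normal no complaints; no evidence of disease", in patients who all have confirmed cancer.

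**Formulas.** The plain test uses Z = (O − E)/√V over all patients. The stratified test uses Z = Σ(O_s − E_s)/√(ΣV_s) over strata s. Both reject when |Z| > 1.96.

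**Hand check with no KPS effect.** Deaths are 49 × (1 − 0.26) = 36.3 in one arm and 49 × (1 − √0.26) = 49 × 0.490 = 24.0 in the other, 60.3 in total. Schoenfeld power is Φ(½ × √60.3 × ln 2 − 1.96) = Φ(2.69 − 1.96) = Φ(0.73), about 77%. The simulation gives about 76%, with 60 to 62 deaths across scenarios.

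**Simulated power at hazard ratio 0.5** (10,000 trials per scenario, standard error about 0.4 points):

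| KPS mix | Hazard per step | Plain | KPS | KPS × largest centre vs rest | KPS × 5 centres |
|---|---|---|---|---|---|
| Thirds | 1.0 | 76.4% | 75.8% | 74.7% | 71.1% |
| Thirds | 1.5 | 73.2% | 75.7% | 74.7% | 70.6% |
| Thirds | 2.0 | 67.4% | 76.1% | 74.5% | 70.2% |
| 5/35/60 | 1.0 | 75.9% | 75.0% | 74.2% | 71.5% |
| 5/35/60 | 1.5 | 75.5% | 76.4% | 75.3% | 73.1% |
| 5/35/60 | 2.0 | 72.6% | 76.2% | 75.3% | 73.1% |

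KPS-stratified minus plain, thirds then 5/35/60:
- no KPS effect: −0.6 and −0.9 points;
- 1.5-fold: +2.5 and +0.9 points;
- 2-fold: +8.7 and +3.6 points.

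**Type I error at 2-fold** (nominal 5%): plain 3.3% (thirds) and 4.1% (5/35/60); KPS-stratified 5.0% and 4.9%.

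**Median Cox hazard ratio for a within-KPS value of 0.50**, plain vs KPS-stratified:
- 1.5-fold: 0.516 vs 0.500 (thirds) and 0.506 vs 0.498 (5/35/60);
- 2-fold: 0.545 vs 0.499 and 0.519 vs 0.497.

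**Different inputs.** A second set of 4,000 to 5,000 runs per scenario used a median OS of 32.6 months (the phase II series in Section 1.1.2) at KPS 90, a 15/35/50% mix and two equal centres. At 2-fold, power was about 73% plain, 79% stratified by KPS and 78% by KPS and centre; the plain hazard ratio was 0.54. At 3-fold it was 62%, 81% and 79%. With six equal centres at 1.5-fold, full KPS-by-centre strata gave 72.1%, against 76.8% plain and 78.2% by KPS alone.

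**The case against.** **The text is silent; it does not say unstratified.** True, and a stratified test may have been intended. But a bare two-group log-rank is normally read as unstratified, and if another test was meant, the sentence still has to say so.

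**The plain test is valid.** It is, so this is a matter of efficiency and pre-specification.

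**No planned estimate is diluted.** Section 12.0 names no hazard ratio. The gap between unstratified and stratified values is largely non-collapsibility: the two describe different quantities, and the plan does not say which it wants. In the 5/35/60 mix the gap (0.506 vs 0.498, or 0.519 vs 0.497) is small beside a standard error of the log hazard ratio of about 2/√60 = 0.26. This stands and limits the weight of the hazard-ratio point.

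**The size is assumed.** The 8.7-point gain needs equal KPS thirds, which sits poorly with the definition of KPS 100. In the 5/35/60 mix the 1.5-fold gain of 0.9 points only equals the cost when KPS has no effect. A hazard ratio of 0.5 is also optimistic. In that mix, plain vs KPS-stratified power at 0.7 is 29.6% vs 30.1% (1.5-fold) and 26.9% vs 31.0% (2-fold); at 0.8 it is 13.9% vs 14.8% and 12.5% vs 14.6%. The comparison is then weak either way. This also stands.

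**Centre is a randomisation factor and should stay.** With only two equal centres, KPS-by-centre strata cost about 1 to 2 points against KPS alone and still beat the plain test when KPS is prognostic. But the plan admits network sites without giving their number, and with five or six centres full strata usually lose power. KPS alone is the safer main analysis.

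**Conclusion.** The concern holds. KPS and centre are used to randomise and appear in no analysis. Under the stated inputs, the plain log-rank test gives up 3.6 to 8.7 points of power at a 2-fold hazard per KPS step and 0.9 to 2.5 points at 1.5-fold. Its actual type I error falls to 3.3% or 4.1% at 2-fold. If KPS is not prognostic, stratifying costs under 1 point. These sizes depend on an assumed hazard ratio, KPS effect, KPS mix and centre split; the lower end is the more plausible if few patients have KPS 100.

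DFS and OS are secondary and unpowered, and the primary toxicity result is not in question. The change should be made because it is cheap, rarely loses much, and settles the choice of test in advance.

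**What to change.** In Section 12.0 and the matching abstract text, replace the sentence with wording such as:

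> DFS and OS will be compared with a log-rank test stratified by KPS group at randomisation (100, 90, 80 and below), with hazard ratios and 95% confidence intervals from a Cox model stratified the same way.

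Add one sensitivity analysis that also stratifies by centre in two levels, the largest centre against all others pooled. Do not use full KPS-by-centre strata: with five centres they changed power against the plain test by −5.3 to +2.8 points. Two-level centre changed it by −1.7 to +7.1. Leave the toxicity Z test as planned.

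The cost is an edit in two places, made before DFS and OS are compared by arm, and 0.6 to 0.9 points of power in the simulated settings if KPS proves not to be prognostic. No new data are required, because KPS group must be known to randomise.

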13.0 SAMPLE HANDLING

13.1 Blood and Urine Samples

Forty (40) ml of blood will be collected, processed, and stored in the RPCI Data Bank and BioRepository at the time points specified in the study calendar. The DBBR will distribute the de-identified samples to the study investigators using established DBBR procedures.

At least 20 and up to 100 ml of spot urine samples will also be collected and stored at -20 °C in the RPCI Data Bank and BioRepository at the time points specified in the study calendar. The DBBR will distribute the deidentified samples to the study investigators using established DBBR procedures.

APPENDIX I

COMMON TERMINOLOGY CRITERIA FOR ADVERSE EVENTS (CTCAE) VERSION

3.0

Pulmonary/Upper Respiratory

Adverse Event	Short Name	1	2	3	4	5
Adult Respiratory Distress Syndrome	ARDS	-	-	Present, intubation not indicated	Present, intubation indicated	Death
Aspiration	_	Asymptomatic ("silent aspiration"); endoscopy or radiographic (e.g., barium swallow) findings	Symptomatic (e.g., altered eating habits, coughing or choking episodes consistent with aspiration); medical intervention indicated(e.g., antibiotics, suction or oxygen)	Clinical or radiographic signs of pneumonia or pneumonitis; unable to treat aliment orally	Life-threatening (e.g., aspiration pneumonia or pneumonitis)	Death
Atelectasis	-	Asymptomatic	Symptomatic (e.g., dyspnea, cough), medical intervention indicated (e.g., bronchoscopic suctioning, chest physiotherapy, suctioning)	Operative (e.g., stent, laser) intervention indicated	Life-threatening respiratory compromise	Death
Bronchospasm, wheezing	-	Asymptomatic	Symptomatic not interfering with function	Symptomatic interfering with function	Life-threatening	Death
Carbon monoxide diffusion capacity	DL _{CO}	90-75% of predicted value	<75-50% of predicted value	<50-25% of predicted value	<25% of predicted value	Death

Chylothorax	-	Asymptomatic	Symptomatic;	Operative	Life-threatening	Death
			thoracentesis or	intervention	(e.g.,	
			tube drainage		hemodynamic	
			indicated		instability or	
					ventilatory	
					support	
					indicated)	
Cough	-	Symptomatic,	Symptomatic	Symptomatic	-	-
		non-narcotic	and narcotic	and		
		medication	medication	significantly		
		only indicated	indicated	interfering		
				with sleep or		
				activities of		
				daily living		
				(ADL)		

Adverse Event	Short Name	1	2	3	4	5
Dyspnea	-	Dyspnea on exertion, but can walk 1 flight of stairs without stopping	Dyspnea on exertion but unable to walk 1 flight of stairs or 1 city block (0.1km) without stopping	Dyspnea with ADL	Dyspnea at rest; intubation/ventilator indicated	Death
Edema, larynx	-	Asymptomatic edema by exam only	Symptomatic edema, no respiratory distress	Stridor; respiratory distress; interfering with ADL	Life-threatening airway compromise; tracheotomy, intubation, or laryngectomy indicated	Death
FEV ₁	-	90-75% of predicted value	<75-50% of predicted value	<50-25% of predicted value	<25% of predicted value	Death
Fistula* - Bronchus - Larynx - Lung - Oral cavity - Pharynx - Pleura - Trachea	-	Asymptomatic, radiographic findings only	Symptomatic, tube thoracostomy or medical management indicated; associated with altered respiratory function but not	Symptomatic and associated with altered respiratory function interfering with ADL; or endoscopic (e.g., stent) or	Life-threatening consequences; operative intervention with thoracoplasty, chronic open drainage or multiple thoracotomies indicated	Death

			interferin a with			
			interfering with	primary		
			ADL	closure by		
				operative		
				intervention		
				indicated		
Hiccoughs	-	Symptomatic,	Symptomatic,	Symptomatic,	-	-
(hiccups,		intervention	intervention	significantly		
singultus)		not indicated	indicated	interfering		
				with sleep or		
				ADL		
Hypoxia	-	-	Decreased O ₂	Decreased O ₂	Life-threatening;	Death
			saturation with	saturation at	intubation or	
			exercise (e.g.,	rest;	ventilation	
			pulse oximeter	continuous	indicated	
			<88%);	oxygen		
			intermittent	indicated		
			supplemental			
			oxygen			
Nasal	_	Asymptomatic	Symptomatic	Stenosis with	Necrosis of soft	Death
cavity/paranasal		mucosal	stenosis or	significant	tissue or bone	
sinus reactions		crusting,	edema/narrowing	nasal		
		blood-tinged	interfering with	obstruction;		
		secretions	airflow	interfering		
				with ADL		

[1		1	1		1
Adverse Event	Short Name	1	2	3	4	5
Obstruction/stenosis of airway - Bronchus - Larynx - Pharynx - Trachea	Airway obstruction	Asymptomatic obstruction or stenosis on exam, endoscopy, or radiograph	Symptomatic (e.g., noisy airway breathing), but causing no respiratory distress; medical management indicated (e.g., steroids)	Interfering with ADL; stridor or endoscopic intervention indicated (e.g., stent, laser)	Life- threatening airway compromise; tracheotomy or intubation indicated	Death
Pleural effusion (non- malignant)	-	Asymptomatic	Symptomatic, intervention such as diuretics or up to 2 therapeutic thoracenteses indicated	Symptomatic and supplemental oxygen, >2 therapeutic thoracenteses, tube drainage, or pleurodesis indicated	Life- threatening (e.g., causing hemodynamic instability or ventilatory support indicated)	Death
Pneumonitis/pulmonary infiltrates	-	Asymptomatic, radiographic findings only	Symptomatic, not interfering with ADL	Symptomatic, interfering with ADL; O ₂ indicated	Life- threatening; ventilatory support indicated	Death
Pneumothorax	-	Asymptomatic, radiographic findings only	Symptomatic; intervention indicated (e.g., hospitalization for observation, tube placement without sclerosis)	Sclerosis and/or operative intervention indicated	Life- threatening, causing hemodynamic instability (e.g., tension pneumothorax); ventilatory support indicated	Death
Prolonged chest tube drainage or air leak after pulmonary resection	-	-	Sclerosis or additional tube thoracostomy indicated	Operative intervention indicated (e.g., thoracotomy with stapling or sealant application)	Life- threatening; debilitating; organ resection indicated	Death

Prolonged intubation	-	-	Extubated	Extubated >72	Tracheostomy	Death
after pulmonary			within 24-72	hrs	indicated	
resection (>24 hours			hrs	postoperatively,		
after surgery)			postoperatively	but before		
				tracheostomy		
				indicated		

Adverse Event	Short	1	2	3	4	5
	Name					
Pulmonary fibrosis** (radiographic changes)	-	Minimal radiographic findings (or patchy or bi- basilar changes) with estimated radiographic proportion of total lung volume that is fibrotic of <25%	Patchy or bi- basilar changes with estimated radiographic proportion of total lung volume that is fibrotic of 25- <50%	Dense or widespread infiltrates/consolidation with estimated radiographic proportion of total lung volume that is fibrotic of 50-<75%	Estimated radiographic proportion of total lung volume that is fibrotic is ≥75%; honeycombing	Death
Vital Capacity	-	90-75% of predicted value	<75-50% of predicted value	<50-25% of predicted value	<25% of predicted value	Death
Voice changes/dysarthria (e.g., hoarseness, loss or alteration in voice, laryngitis)	-	Mild or intermittent hoarseness or voice change, but fully understandable	Moderate or persistent voice changes, may require occasional repetition but understandable on telephone	Severe voice changes including predominantly whispered speech; may require frequent repetition or face-to- face contact for understandability; requires voice aid (e.g., electrolarynx) for \leq 50% of communication	Disabling; non- understandable voice or aphonic; requires voice aid (e.g., electrolarynx) for >50% written communication	Death
Pulmonary/Upper Respiratory – Other	-	Mild	Moderate	Severe	Life- threatening; disabling	Death

*A fistula is defined as an abnormal communication between two body cavities, potential spaces, and/or the skin. The site indicated for a fistula should be the site from which the abnormal process is believed to have arisen.

**Fibrosis is usually a "late effect" seen >3 months after radiation or combined modality therapy (including surgery). It is thought to represent scar/fibrotic lung tissue. It may be difficult to distinguish from pneumonitis that is generally seen within 3 months of radiation or combined modality therapy.

